## 5. PATIENT SELECTION

### 5.1. Inclusion Criteria

All ischemic stroke patients admitted to Regions Hospital within the study period will be identified.

- Age  $\geq$  18 years
- Patient has suffered an ischemic stroke
- Patient should be ambulatory (non-disabling stroke) to be able to participate in the CCR exercise program
- Patient is able to start cardiac rehabilitation within 3 months of stroke

### 5.2. Exclusion Criteria

A subject will not be included for consideration in this study if any of the following criteria are met:

- No baseline (index admission for ischemic stroke) MRI completed
- Life expectancy  $<$  1-year

- Presence of brain hemorrhage: intracerebral hemorrhage, subarachnoid hemorrhage, subdural hematoma, or epidural hematoma
- Concurrent diagnosis of seizure disorder
- Patient with moderate or severe neurologic deficits, limiting their ability to participate in the CCR exercise program
- Cardiopulmonary conditions preventing the patient from participation, such as severe heart failure, severe aortic stenosis, and exercise-induced asthma
- Patient with cognitive dysfunction impairing their ability to follow directions
- Anticipated procedures such as carotid stenting, carotid endarterectomy, and intracranial aneurysm coiling
- Patient unable to commit to the frequent visits of the CCR program
- Participation in other interventional research (observational research is allowed)
- Unable to have brain MRI
- Non-English speaker
- Pregnant women

## **6. STUDY ASSESSMENTS AND PROCEDURES**

### **6.1. Study Assessments**

#### **6.1.1. National Institutes of Health Stroke Scale (NIHSS)**

NIHSS is a tool used to evaluate stroke severity. The total score ranges from 0-42, with a higher score indicating a more severe stroke.

#### **6.1.2. Modified Rankin Scale (MRS)**

MRS is a tool used to evaluate the level of disability after stroke. The assessment ranges from 0-6, where 0 is no symptoms at all and 6 is dead.

#### **6.1.3. European Quality of Life Scale (EQ-5D)**

The EQ-5D is a tool used to measure health-related quality of life. The tool includes the following dimensions: mobility, self-care, usual activities, pain/discomfort, and anxiety/depression. The scale ranges from 5-25, with 5 indicating no problems and 25 indicating extreme problems.

#### **6.1.4. Patient Health Questionnaire (PHQ-9)**

The PHQ-9 is a tool used to assess depression severity. The scale ranges from 1-27, with a score of 1-4 indicating minimal depression and a score of 20-27 indicating severe depression.

### **6.1.5. Montreal Cognitive Assessment (MoCA)**

The MoCA is a brief cognitive screening tool for detecting cognitive impairment or dementia. The assessment measures multiple cognitive domains including attention, concentration, executive function, memory, language, visuoconstructional skills, conceptual thinking, calculations, and orientation. The scale ranges from 0-30, with a lower score indicating worse cognitive function.

Because the MoCA is assessed three times within 6-7 months, we plan to use different versions to reduce the possibility of a learning effect. Occupational therapy completes a MoCA assessment during inpatient stroke admission and utilizes version 7.1, so the MoCA score will be extracted from the patient's chart. For the 3-month clinic assessment we will use version 7.2 and for the 6-month clinic assessment we will use version 7.3. These are standardized approved versions.

## **6.2. Procedures**

### **6.2.1. Visit 1: Screening/Baseline (Regions Hospital or HealthPartners Neuroscience Center)**

- Obtain written informed consent from subject (or subject's legally authorized representative) prior to any study related procedures.
- Review Inclusion/Exclusion criteria.
- Review medical history, as it pertains to inclusion/exclusion criteria, such as research diagnosis, disease severity, and course of stroke.
- Obtain demographic information.
- Obtain details of medications.
- Collect vital signs; heart rate, blood pressure, oxygen saturation, height, and weight.
- Obtain NIHSS score.
- Obtain MRS score.
- Administer MoCA if not previously measured.
- Administer PHQ-9.
- Retrospectively collect medical information on laboratory tests, vascular imaging, MRI, and echocardiogram.

### **6.2.2. Visit 2: 6-Week Phone Call (From start of cardiac rehabilitation)**

- Gather information on cardiac rehabilitation progress.
- Review current medications.
- Record AEs/SAEs.
- 3-month clinic visit will be scheduled 3-months since start of cardiac rehabilitation.

### **6.2.3. Visit 3: 3-Month Clinic Visit**

- Collect vital signs.
- Review current medications.

- Administer MoCA.
- Complete EQ-5D.
- Complete PHQ-9.
- Obtain NIHSS score with physician.
- Obtain MRS score with physician.
- Record AEs/SAEs.
- 6-month MRI and clinic visit will be scheduled 6-months since start of cardiac rehabilitation.

#### **6.2.4. Visit 4: 6-Month MRI and Clinic Visit**

- Undergo MRI.
- Collect laboratory samples; lipid panel, basic metabolic panel, coagulation panel, glycosylated hemoglobin, and Cotinine.
- Collect vital signs.
- Review current medications.
- Administer MoCA.
- Complete EQ-5D.
- Complete PHQ-9.
- Obtain NIHSS score with physician.
- Obtain MRS score with physician.
- Record AEs/SAEs.

\*This visit may be separated into 2 visits, if needed.

#### **6.3. Early Withdrawal**

If a patient drops out of the study or stops attending CCR classes, the research staff will call the patient to ask why he or she stopped attending CCR. If the research staff is unable to reach the patient after two phone call attempts, they will attempt to reach the patient at his or her next Neuroscience Center clinic visit to obtain a drop out reason. In addition, adverse or serious adverse events will be monitored by the study staff throughout the study.

#### **6.4. Safety**

For all safety assessments described below, any clinically significant change will be recorded as an AE or SAE.

#### **6.5. Vital Signs**

Vital signs and O2 saturation will be recorded at visits 1, 3, and 4 and recorded prior to the MRI and blood draw. For within subject consistency, brachial artery pressure will be obtained in the routine fashion and the same arm will be used for all study measurements.

Blood pressure and heart rate will be measured after subject has been sitting quietly for a minimum of 5 minutes. Vitals signs and O2 saturation will be monitored by clinical staff during each visit of the study.

## **6.6. Weight**

Body weight will be measured at visits 1, 3, and 4, without heavy outer clothing or footwear.

## **6.7. MRI**

A standard MRI will be performed on all subjects at visit 4. This will be performed prior to the clinic visit.

## **6.8. Laboratory Samples**

During visit 4, participant will undergo a blood draw. The following laboratory tests will be performed: lipid panel, basic metabolic panel, coagulation panel, and glycosylated hemoglobin. Any abnormal laboratory results at this visit will be communicated by the Principal Investigator or study staff to the physician and the patient. This can be obtained before or after MRI and clinic evaluations.

# **7. SUBJECT COMPLETION AND WITHDRAWAL**

## **7.1. Subject Completion**

Subjects completing all 3 study visits and 75% attendance of CCR sessions will be considered to have completed study.

## **7.2. Subject Withdrawal**

Subjects may withdraw from study at any time for any reason without penalty or be terminated from the study by the clinical investigator (see provisions for termination by study team.) The investigational team will document the reason(s) for withdrawal. In the event a subject chooses to withdraw from study before Visit 4, the safety procedures described in Section 6.2.4. will be collected within 14 days following subject's decision to withdraw. For all subjects who withdraw, all final safety assessments will be collected regardless of time elapsed since the previous visit. In addition to final visit, subjects who withdraw early will be contacted within 7 days by study staff via telephone to assess for the development of any new and/or ongoing AEs and concomitant medications. Efforts will be made to recruit subjects to replace any withdrawals so as to maintain an n=17.

Subject's participation may be terminated at the discretion of the investigator. Individuals may be withdrawn for the following reasons:

- Clinically significant adverse events
- Lost to follow-up
- Protocol violations
- Inability to tolerate study intervention
- Other

## **8. ADVERSE EVENTS (AE) AND SERIOUS ADVERSE EVENTS (SAE)**

### **8.1. Definition of AE**

An adverse event is any symptom, sign, illness or experience which develops or worsens in severity during the course of the study. Interval development of illnesses or injuries will be regarded as adverse events. Abnormal results of diagnostic procedures are considered to be adverse events if the abnormality:

- Results in study withdrawal
- Is associated with clinical signs or symptoms
- Leads to treatment or to further diagnostic tests
- Is considered by the investigator to be of clinical significance

### **8.2. Definition of SAE**

Adverse events are classified as either serious or non-serious. A serious adverse event is any event that results in:

- Death
- Life-threatening situation
- Hospitalization or prolongation of hospitalization
- Disability or incapacitation
- Other events determined by investigator to be medically significant in which subject's well-being is jeopardized (e.g. events that have high likelihood of escalating to the point of meeting criteria outlined above)

#### **8.2.1. Clinical Laboratory Abnormalities and Other Abnormal Assessments as AEs and SAEs**

Any new abnormal, vital, examination, or laboratory finding judged clinically significant by the investigator will be documented as an AE or SAE, if meeting the definitions for such. Abnormal lab findings or other abnormal assessments associated with the disease under study will not be considered AEs or SAEs unless more severe than expected, as judged by the investigator.

#### **8.2.2. Time Period and Frequency of Detecting AEs and SAEs**

Upon consenting, a subject is considered to be a participant in the study, and until that person either withdraws or completes study, AEs and SAEs will be recorded. The investigational team will promptly report any AE/SAE as required per federal guidelines.

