## **9.4. Secondary Analyses**

For the secondary analyses, we will explore the potential benefits of cardiac rehabilitation for stroke patients by describing the 6-month rates of recurrent stroke, myocardial infarction, hospital readmission for a cardiovascular or cerebrovascular indication, silent stroke on MRI and death. We will assess the individual and composite event rates by calculating the mean and 95% confidence interval. This will provide information to allow us to power a larger study.

Additionally, we plan to descriptively compare weight, BMI, blood pressure, and laboratory values at the beginning and end of the study. We will do this by calculating the mean and 95% confidence intervals for these values.

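### Six-month event rates are simple means with no stated denominator, although events are not followed beyond about two weeks after withdrawal, so the rates may be biased

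*Combined protocol and SAP*

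**What the plan says.** - **Recording window.** Section 8.2.2 starts at consent and says that "until that person either withdraws or completes study, AEs and SAEs will be recorded".
- **After withdrawal.** Section 7.2 adds two contacts. Safety procedures "will be collected within 14 days following subject's decision to withdraw", and patients who leave early "will be contacted within 7 days by study staff via telephone to assess for the development of any new and/or ongoing AEs". Nothing later is described.
- **A general statement.** Section 6.3 says that "adverse or serious adverse events will be monitored by the study staff throughout the study", without saying whether this covers patients who have withdrawn.
- **Reasons for leaving.** Section 7.2 lets the investigator end participation for several reasons, the first being "Clinically significant adverse events". Inability to tolerate the intervention is another.
- **Replacement.** Section 7.2 also says: "Efforts will be made to recruit subjects to replace any withdrawals so as to maintain an n=17".
- **The endpoint.** Section 9.4 plans on "describing the 6-month rates of recurrent stroke, myocardial infarction, hospital readmission for a cardiovascular or cerebrovascular indication, silent stroke on MRI and death". Individual and composite rates are to be means with 95% confidence intervals, and they are to inform the power of a larger study.
- **Missing data.** Section 9.2 rules out imputation. No section gives a denominator, a censoring rule or a time-to-event method for the event rates.

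**The concern.** A rate labelled as 6-month needs event status at 6 months for everyone in its denominator. Under sections 7.2 and 8.2.2, a patient who withdraws at week 6 is observed for at most about 8 of 26 weeks. Section 9.4 does not say whether that patient counts as event-free, is excluded, or gives way to a replacement. Each choice yields a different rate. Because withdrawal may follow an adverse event or poor tolerance of the program, those who leave may be at higher risk than those who stay.

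Two uses are affected. A distorted event rate carries into the sample size of the larger trial. The study purpose also includes safety, and counting unobserved time as event-free would favour CCR. The confidence interval in section 9.4 reflects sampling error only and gives no sign of missing follow-up.

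**Working it through.** **The plan's own precision figure.** Section 9.5 gives ±20.2 points for a 75% completion rate with n = 17. The half-width 1.96 × √(p(1−p)/17) is 20.16 points at the nearest attainable count, 13/17, and 20.6 at exactly 75%. The figure reproduces, but it concerns completion, not events.

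**Inputs.** n = 17 and 6 months (182 days) of follow-up come from the plan, as does the 14-day closing assessment. The plan gives no withdrawal rate or event rate, so these are assumptions: 4 of 17 withdraw after a fraction f = 0.25 to 0.50 of follow-up; completers' 6-month risk r = 0.10 to 0.20; withdrawers' hazard is h = 1 to 3 times as high; hazards are constant. Let λ = −ln(1−r) and c = f + 14/182, the fraction of follow-up observed in withdrawers.

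**1. Withdrawn patients counted as event-free after the last contact**

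- True rate = [13r + 4(1 − e^(−hλ))]/17
- Reported rate = [13r + 4(1 − e^(−hλc))]/17

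Example with r = 0.15, h = 2, λ = 0.1625:

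- True: (1.95 + 4 × 0.2775)/17 = 18.0%.
- f = 0.25, c = 0.327: (1.95 + 4 × 0.1008)/17 = 13.8%.
- f = 0.50, c = 0.577: (1.95 + 4 × 0.1710)/17 = 15.5%.

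The shortfall is 4 × (0.2775 − 0.1008) = 0.7 of a patient, or 4 × (0.2775 − 0.1710) = 0.4. Over the whole range, the relative understatement runs from 9% (r = 0.20, h = 1, f = 0.50: 18.1% against 20.0%) to 29% (r = 0.10, h = 3, f = 0.25: 10.0% against 14.0%).

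**2. Event-free withdrawals excluded, earlier events kept**

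Reported rate ≈ [13r + 4q]/[13 + 4q], with q = 1 − e^(−hλc).

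| r = 0.15 | True | f = 0.25 | f = 0.50 |
|---|---|---|---|
| h = 1 | 15.0% | 16.3% | 17.3% |
| h = 2 | 18.0% | 17.6% | 19.2% |

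At equal risk the rate is too high. With higher-risk withdrawers, the two errors partly cancel.

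**3. Withdrawn patients dropped or replaced**

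Take 3 events in 17, one of which leads to withdrawal. All enrolled: 3/17 = 17.6%. Completers only: 2/16 = 12.5%. After replacement by an event-free patient: 2/17 = 11.8%.

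**4. What Kaplan-Meier alone would do**

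Estimate = 1 − {[13e^(−λc) + 4e^(−hλc)]/17} × e^(−λ(1−c)). With r = 0.15 and h = 2 this gives 16.0% (f = 0.25) to 16.8% (f = 0.50) against 18.0%. It is unbiased at h = 1. At h = 3 it stays about 9% to 19% low over the range. It corrects for incomplete follow-up but not for withdrawal related to risk.

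**5. Scale**

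For 3/17 the exact 95% CI is 3.8% to 43.4%. With 3 events and 4 event-free withdrawals, best- and worst-case bounds are 3/17 = 17.6% and 7/17 = 41.2%.

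**The case against.** A reader might infer that event recording simply stops at withdrawal and that the rates will therefore be biased low. The documents do not support that reading, for four reasons.

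- Section 7.2 provides two contacts after withdrawal, and section 6.3 speaks of monitoring throughout the study. This shortens the gap but does not close it. Section 8.2.2 is the specific rule on the recording window, and section 6.3 does not clearly override it. The three sections need reconciling.
- The direction is not fixed. Section 9.2 rules out imputation, and scoring unknown status as no event would itself be a form of imputation. With no denominator stated, excluding event-free withdrawals is equally open, and step 2 shows that this can raise the rate.
- An event that triggers withdrawal happens before it and is recorded. It is lost only if that patient is dropped or replaced in the analysis, which section 7.2 leaves possible.
- It is also tempting to take 4 withdrawals in 17 as implied by the 75% completion rate in section 9.5. It is not. Completion requires attendance, MRI, labs and the final visit, so a non-completer may still be observed for all 6 months.

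It can also be said that these rates are secondary, descriptive and without a comparator, and that the shortfall in the example is under one patient. That stands, and it limits the weight of the point. It does not remove it, because section 9.4 gives the rates a stated use in planning.

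**Conclusion.** The gap is real. As written, event status between about two weeks after withdrawal and month 6 is not collected, the denominator is undefined (including whether replaced patients count), and the estimator ignores incomplete follow-up. The 6-month rates may be biased, most plausibly downward, but the sign depends on a choice the plan does not make.

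The 9% to 29% relative understatement holds only if withdrawn patients are counted as event-free, and it rests on assumed numbers and timing of withdrawals, assumed risks and constant hazards. With 17 patients it is small beside sampling error. This is a worthwhile, inexpensive improvement to a secondary descriptive endpoint. It does not touch the primary completion analysis.

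**What to change.** 1. Reconcile sections 6.3, 7.2 and 8.2.2 on how long events are collected after withdrawal.
2. In sections 8.2.2 and 9.4, state that recurrent stroke, MI, readmission for a cardiovascular or cerebrovascular cause, and death are ascertained to 6 months from the medical record for every patient who started CCR, including withdrawn and replaced patients, unless the patient refuses record follow-up.
3. Make all patients who started CCR the denominator. State the origin of the 6-month clock, since section 4 counts from the baseline visit and section 6.2.3 from the start of CCR.
4. For patients still incompletely followed, report a Kaplan-Meier 6-month rate with 95% CI, state that it assumes uninformative censoring, and give best- and worst-case bounds beside it.
5. Report silent stroke separately among patients with a 6-month MRI, because it is known only from that scan and has no event time. Report the composite with and without it.

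**Cost.** No new visits are needed, only a short chart review for the few who withdraw and a different SAS procedure. Records are already a data source: at baseline staff are to "Retrospectively collect medical information on laboratory tests, vascular imaging, MRI, and echocardiogram", and the COVID-19 amendment takes labs from records. The review must be finished before identifiers are destroyed at closure (section 10.6). Consent must allow record follow-up. The synopsis lists enrollment as complete, so check the consent already signed; where it does not allow this, the bounds in item 4 apply. Events treated outside the health system may still be missed.

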## **9. DATA ANALYSIS AND STATISTICAL CONSIDERATIONS**

### **9.1. Statistical Analysis**

The statistical analysis plan was written by [name], Biostatistician at the HealthPartners Institute. She will also perform the statistical analyses for the study.

## **9.2. Preliminary Analysis**

Descriptive statistics, such as mean and standard deviation (for continuous variables) and frequency (for categorical and binary variables) will be computed for all demographic variables. Population demographics will include age, gender, stroke type, labs, BMI, and others.

No imputation for missing data or adjustment for multiple comparisons will be done as they were deemed too conservative for this feasibility study. All statistical analyses will be performed in SAS 9.4 with  $p<0.05$  considered to be statistically significant.

## **9.3. Primary Analysis**

The primary goal of this feasibility study will be to determine the study completion rate. This will be defined as 75% attendance at CCR sessions, acquisition of 6-month MRI and labs, and attendance of end of study visit. We will calculate and report the 95% confidence interval for this rate. We will also report the number of charts reviewed, the number of patients screened for inclusion/exclusion criteria, the number of patients contacted for the study, the number of patients that agreed to participate, the number of patients that started CCR, and the number of patients that dropped out or completed CCR. We will also describe reasons for non-completion.

## **9.4. Secondary Analyses**

For the secondary analyses, we will explore the potential benefits of cardiac rehabilitation for stroke patients by describing the 6-month rates of recurrent stroke, myocardial infarction, hospital readmission for a cardiovascular or cerebrovascular indication, silent stroke on MRI and death. We will assess the individual and composite event rates by calculating the mean and 95% confidence interval. This will provide information to allow us to power a larger study.

Additionally, we plan to descriptively compare weight, BMI, blood pressure, and laboratory values at the beginning and end of the study. We will do this by calculating the mean and 95% confidence intervals for these values.

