A few studies have attempted to integrate CCR after stroke. These studies showed that CCR has short-term beneficial effect on vascular risk factors control (blood pressure, lipid profile, body mass index) and exercise endurance. However, none of these studies specifically evaluated the effect that CCR has on clinical endpoints such as stroke recurrence and hospital readmission.

The overall goal of this study is to assess the feasibility of stroke patient participation in Regions Hospital's CCR program. Our study will examine the ability of stroke patient to complete the current CCR program (provided as standard of care by cardiology department). The program consists of 3 sessions per week over 12 weeks. Exploratory endpoints will be the event rate of recurrent stroke at 6 months, MI, death, hospital readmission for a cardiovascular or cerebrovascular indication, and silent stroke on MRI. These analyses will help us with our future power analysis for a subsequent larger trial. The experience, workflow, and the knowledge gained from this study will be used to design a larger study, comparing CCR with conventional post-stroke treatment.

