## **9.5. Study Power**

Our sample size is based on the capacity of the CCR course as deemed by the cardiac rehabilitation program. With a sample size of 17, we will be able to estimate a completion rate of 75% to within a 95% confidence interval of  $\pm 20.2\%$ .

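### Sections 9.3 and 9.4 promise 95% intervals for binary rates in 17 patients but name neither the interval method nor the denominator, although withdrawals may be replaced (minor)

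*Combined protocol and SAP*

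**What the plan says.** On the completion rate, section 9.3 says "We will calculate and report the 95% confidence interval for this rate". On the events (recurrent stroke, myocardial infarction, readmission, silent stroke on MRI, death), section 9.4 says "We will assess the individual and composite event rates by calculating the mean and 95% confidence interval". It describes weight, BMI, blood pressure and laboratory values in nearly the same terms: "We will do this by calculating the mean and 95% confidence intervals for these values". No interval method is named in any section; section 9.2 gives only the software and the significance level.

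The one precision figure is in section 9.5: with 17 patients, "we will be able to estimate a completion rate of 75% to within a 95% confidence interval of" ±20.2%.

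On the denominator, section 7.2 says "Efforts will be made to recruit subjects to replace any withdrawals so as to maintain an n=17", and section 9.2 says "No imputation for missing data or adjustment for multiple comparisons will be done". The synopsis recruits until the 17th patient is enrolled in the rehabilitation programme (CCR), section 4 speaks of seventeen patients consented, and section 8.2.2 makes a patient a participant on consent. Section 9.3 lists counts to be reported, including those who agreed, those who started CCR, and those who dropped out or completed it. It does not say which count is the denominator.

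**The concern.** The interval for the completion rate is the only inferential output of the primary analysis. Of the exploratory event rates the Introduction says "These analyses will help us with our future power analysis for a subsequent larger trial", and section 9.4 repeats that purpose. At this sample size the methods that fit the text give clearly different limits, and with the method open it could be chosen after the counts are known. The worst case is a rare event. If none is seen, a mean-based interval has zero width and tells the planner of the next trial that the rate is known exactly.

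The denominator bears on the primary endpoint directly. A patient who withdraws is normally a non-completer. If that patient is replaced and then left out of N, the completion rate is inflated by a procedure the plan itself allows.

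**Working it through.** **Inputs.** n = 17 and 75% (section 9.5); 95% level (9.3, 9.4), taken as two-sided from the ± form in 9.5; z = 1.960; t with 16 df = 2.120.

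**Step 1: the figure in 9.5.** Wald half-width = z × √(p(1−p)/n).
- At p = 0.75: 1.960 × √(0.1875/17) = 0.2058, or ±20.6 points.
- 75% of 17 is 12.75 patients, which cannot occur. The nearest count is 13/17 = 76.5%: 1.960 × √(0.7647 × 0.2353/17) = 0.2016, or ±20.2 points.

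The printed figure therefore agrees with Wald at 13/17. Other half-widths at exactly 75% are 22.9 (t, using the sample SD), 19.6 (Agresti-Coull), 19.2 (Wilson) and 21.9 (exact); none is 20.2. That 13/17 is the source is an inference, since the document does not say.

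The exact (Clopper-Pearson) interval at 13/17 is 50.1% to 93.2%. That is 76.5 − 50.1 = 26.4 points below the estimate and 93.2 − 76.5 = 16.7 above it, an asymmetry that a single ± hides. Wilson gives 52.7% to 90.4%.

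**Step 2: event rates, n = 17.** The t form is p ± t × s/√n, with s the SD of the 0/1 values.

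| Events | Wald (%) | t lower (%) | Wilson (%) | Exact (%) |
|---|---|---|---|---|
| 0 | 0 to 0 | 0 | 0 to 18.4 | 0 to 19.5 |
| 1 | −5.3 to 17.1 | −6.6 | 1.0 to 27.0 | 0.1 to 28.7 |
| 2 | −3.6 to 27.1 | −5.3 | 3.3 to 34.3 | 1.5 to 36.4 |
| 3 | −0.5 to 35.8 | −2.6 | 6.2 to 41.0 | 3.8 to 43.4 |

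The exact upper limit at 0 events is 1 − 0.025^(1/17) = 0.195. From 4 events the mean-based lower limits are positive (Wald 3.4%, t 1.0%).

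**Step 3: coverage.** The documents give no event rates, so true rates of 5% and 10% are assumed. At 5%, the chance of no event in 17 patients is 0.95^17 = 41.8%, and each such result would be reported by Wald as 0% to 0%. Summing binomial probabilities over the counts whose interval contains the true rate gives:
- Wald: 58.1% at 5% and 82.9% at 10%
- Wilson: 95.0% and 97.8%
- Exact: 99.1% and 97.8%

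At a completion rate of 75%, Wald coverage is 93.8%.

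**Step 4: completion-rate lower limit, exact against Wald.** 13/17: 50.1% against 56.3%. 15/17: 63.6% against 72.9%. 17/17: 80.5% against 100%.

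**Step 5: denominator.** The documents give no number of withdrawals, so three replaced is an illustration.
- Replaced patients left out: 13/17 = 76.5% (exact 50.1% to 93.2%).
- Replaced patients kept: 13/20 = 65.0% (exact 40.8% to 84.6%).

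For silent stroke, missing MRIs also move the limit. With 0 events the exact upper limit is 19.5% on 17 scans, 21.8% on 15 and 24.7% on 13.

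**The case against.** The mean of a 0/1 variable is the proportion, so 9.4 is loosely worded rather than wrong, and an exact or Wilson interval would comply with it. A reader might infer from the ± in 9.5 that the analysis is committed to Wald. The documents do not say so, and the zero-width and negative limits above arise only if a mean-based form is used. Mid-range differences are also modest. At 13/17 the lower limits are 50.1% (exact), 52.7% (Wilson), 54.0% (t) and 56.3% (Wald), a spread of about 6 points on an interval about 40 points wide. All of this stands.

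A reader might also take ±20.2% for a calculation error that undermines the sample size. That is not supported. The gap from ±20.6% is 0.4 points, 13/17 explains it, and 9.5 says that 17 was set by programme capacity.

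Nor do the documents support a reading that dropouts would be concealed. The counts promised in 9.3, with reasons for non-completion, would let a reader rebuild the main candidate denominators. This limits the harm but does not fix in advance which rate is the primary result.

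**Conclusion.** The point holds as a minor one. No method is named for any binary interval, and at n = 17 the omission matters most for rare events: 0% to 0% against an upper limit of 19.5% at no events, and impossible negative limits at 1 to 3. The denominator gap could inflate the primary rate, by 11.5 points (76.5 − 65.0) in the illustration. That size rests on an assumed three replacements, and the coverage figures rest on assumed event rates. The mismatch in 9.5 is a matter of labelling with no consequence of its own. Severity stays low because this is a single-arm feasibility study and no test or go/no-go rule uses these intervals.

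**What to change.** In 9.3 and 9.4, report every binary rate as n/N with a two-sided 95% Clopper-Pearson interval; Wilson is acceptable if it is named as the single method. Keep mean-based intervals for continuous variables. Then fix N:

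- **Completion rate:** every patient who started CCR, including those who withdrew and were replaced, with the rate among all consented patients beside it. Enrolled alone is too ambiguous a term here.
- **Clinical events and the composite:** the same patients who started CCR, counting observed events, with the number lacking 6-month follow-up or MRI printed beside the rate.
- **Silent stroke:** patients with a 6-month MRI. Also give a composite without silent stroke.

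Do not use a composite denominator that keeps unassessed patients only if they had an event, because inclusion then depends on the outcome. For illustration, take 17 patients, 13 with MRI, and 2 events, one of them in a patient without MRI. That rule gives 2/14 = 14.3%, against 2/17 = 11.8% over all patients and 1/13 = 7.7% among those scanned.

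Restate 9.5 as: *With 17 patients, 13 completers (76.5%) would give an exact 95% CI of 50.1% to 93.2%.*

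The cost is wording only; sample size, visits and data collection do not change. Exact intervals are somewhat wider (43.1 points in total at 13/17, against 40.3 for Wald and 37.7 for Wilson), and the reported completion rate may be lower. The change should be made before the counts are analysed.
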